## 5.9. Treatment Exposure

Treatment exposure will be summarized and listed using safety analysis set.

Treatment exposure is defined as the time from when the patient is randomized at Visit 3 and receives study drug until the patient either permanently discontinues from investigational product or completes the treatment period.

Duration of exposure will be categorized into the following groups: >0 weeks,  $\geq$ 16 weeks, and  $\geq$ 52 weeks. These categories will be summarized as frequency by treatment.

## 5.10. Efficacy Analysis

#### 5.10.1. Primary Efficacy Analysis

Analysis of HbA1c based on MMRM will be summarized by treatment group using FAS. The primary analysis model is shown in 5.10.1.2.

#### 5.10.1.1. Additional Analyses for Primary Endpoint

Analysis of HbA1c based on MMRM will be summarized by treatment group using PPS. Also, analysis of HbA1c based on ANCOVA will be summarized by treatment group using FAS.

#### 5.10.1.2. Primary Analysis Model

The primary analysis model will be an MMRM for HbA1c change from baseline to 16 weeks (Visit 7) using REML with treatment, insulin regimen (basal insulin, premixed insulin, or

basal/mealtime insulin), visit, and treatment-by-visit as fixed effects, baseline HbA1c as a covariate, and patient as a random effect.

An unstructured covariance structure will be used to model the within-patient variability and implicitly adjust for missing data. If this analysis fails to converge, the following covariance structures will be tested in order:

- Toeplitz with heterogeneity
- Autoregressive with heterogeneity, by visit
- Compound symmetry with heterogeneous variances, by visit
- Toeplitz
- Autoregressive
- Compound symmetry without heterogeneous variances, by visit.

The first covariance structure that converges will be used. The Kenward-Roger approximation will be used to estimate denominator degrees of freedom. Significance tests will be based on least squares (LS) means using Type III sum of squares.

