### **10.3.3. Efficacy Analyses**

#### **10.3.3.1. Primary Analyses**

The primary analysis model will be an MMRM for HbA1c change from baseline to 16 weeks (Visit 7) using REML with treatment, insulin regimen (basal insulin, premixed insulin, or basal/mealtime insulin), visit, and treatment-by-visit as fixed effects, baseline HbA1c as a covariate, and patient as a random effect.

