## 5. A Priori Statistical Methods

## 5.1. Determination of Sample Size

A total of approximately 160 patients (dulaglutide: 120 patients; placebo: 40 patients) will be randomized to have approximately 136 completers (dulaglutide : 102 patients; placebo: 34 patients) to show dulaglutide is superior to placebo with more than 99% power assuming a treatment difference of 1.0% in HbA1c reduction, standard deviation (SD) = 1.0%, and dropout rate of 15%. The screen failure rate is estimated as 20%. Approximately 200 patients will be screened.

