#### 5.2. General Considerations

Statistical analysis of this study will be the responsibility of Lilly or its designee. Any change to the data analysis methods described in the protocol will require an amendment ONLY if it changes a principal feature of the protocol. Any other change to the data analysis methods described in the protocol, and the justification for making the change, will be described in the clinical study report (CSR). Additional exploratory analyses of the data will be conducted as deemed appropriate.

All analyses will be implemented using Version 9.1.3 SAS or higher.

Continuous data will be summarized in terms of the number of observations (n), mean, standard deviation (SD) and/or standard error of the mean (SEM), median, minimum (Min), and maximum (Max).

Categorical data will be summarized in terms of the number of observations (n), frequency count, and percentages. Percentages will be rounded to one decimal place. Percentages will not be presented for zero counts. Unless noted otherwise, percentages will be calculated using n (the number of observations with non-missing values) as denominator.

For efficacy analysis based on mixed-model for repeated measures (MMRM), summary statistics will be provided for the observed value and change from baseline value for each arm based on MMRM. Also, for efficacy analysis, statistical tests (including MMRM and ANCOVA) will only be conducted during the double-blind primary treatment period at each visit (i.e. Visit 4, 5, 6 and 7) and will not be conducted for time point after Visit 7.

For safety analysis, summary statistics will be provided for each arm during the both doubleblind primary treatment period (i.e. Visit 3 to 7) and entire study period (i.e. Visit 3 to 13). Table GBGF 5.1 gives the treatment groups to be displayed for each treatment period.

Unless otherwise specified, all tests of treatment effects will be conducted at a 2-sided alpha level of 0.05, and confidence intervals (CIs) will be calculated at 95%, 2-sided. All tests of interactions between treatment groups and other factors will be conducted at a 2-sided alpha level of 0.10. There will be no multiplicity adjustment for pairwise treatment comparisons.

List of analysis (LOA) will contain the list of all tables, figures and listings (TFLs), and will be provided separately.

			Between-Group Comparison When
Treatment Period	Treatment Groups	Abbreviation	Applicable
Double-blind	Placebo	Plc	Dula vs Plc

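### The primary MMRM uses one baseline HbA1c slope for all four visits; if the slope steepens over time, the Week 16 contrast is under-adjusted and loses some precision

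*SAP*

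**What the plan says.** Both documents give the same primary model for change in HbA1c. SAP 5.10.1.2 lists treatment and insulin regimen, then "visit, and treatment-by-visit as fixed effects, baseline HbA1c as a covariate". Protocol 10.3.3.1 likewise lists treatment and insulin regimen, then "visit, and treatment-by-visit as fixed effects, baseline HbA1c as a covariate, and patient as a random effect". Baseline HbA1c enters once, and only treatment is crossed with visit. On the covariance, SAP 5.10.1.2 states: "An unstructured covariance structure will be used to model the within-patient variability and implicitly adjust for missing data". SAP 5.2 places the efficacy tests at Visits 4 to 7, which are Weeks 4, 8, 12 and 16.

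The missing term does not read as shorthand. The subgroup models in Protocol 10.3.7 and SAP 5.15 name their by-visit interactions one by one.

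Three other passages bear on the point:

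- Protocol 7.2 stratifies randomization by insulin regimen and by Visit 2 HbA1c (below 8.5%, or 8.5% and above).
- Protocol 5.4 says that HbA1c reduction was stable after 14 weeks in Japanese Phase 3 studies.
- SAP 5.10.1.3 adds an ANCOVA at Week 16, with last observation carried forward, as the secondary analysis of the primary endpoint.

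**The concern.** HbA1c responds gradually. If the mean response settles only after about 14 weeks, the dependence of change on baseline may also be weaker at Week 4 than at Week 16. A model with one slope must then compromise across visits. Under an unstructured covariance the compromise is a weighted average that favours the less variable visits. If early visits are the less variable ones, the Week 16 contrast is adjusted with a slope that is too shallow.

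Two things would be lost at Week 16. Some outcome variance that baseline could explain stays in the comparison and widens the interval. Part of any chance difference in baseline HbA1c between the arms also stays in the estimate. Neither loss is needed, since a single extra interaction removes both.

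**Working it through.** **The plan's own figure.** SAP 5.1 gives 102 and 34 completers, a difference of 1.0 and an SD of 1.0, "to show dulaglutide is superior to placebo with more than 99% power". SAP 5.2 sets two-sided alpha at 0.05. The SE is 1.0 × √(1/34 + 1/102) = 0.1980, so power is Φ(1/0.1980 − 1.96) = Φ(3.09) = 99.90%. The noncentral t with 134 df gives 99.89%. The stated power reproduces.

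**Formulas, complete data.** Let b hold the true baseline slopes at the four visits, S the residual covariance given baseline, sx the baseline SD, and s16 the Week 16 residual SD.

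- Pooled slope: c = 1′S⁻¹b / 1′S⁻¹1.
- Week 16 variance with one slope: (s16² + (b16 − c)² sx²)(1/34 + 1/102).
- Week 16 variance with baseline-by-visit: s16² (1/34 + 1/102).
- Imbalance left uncorrected: |b16 − c| times the baseline difference between arms.

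**Assumed inputs.** None of these is in the documents. Baseline SD is 0.8 and Week 16 residual SD is 0.9. The Week 4 slope runs from -0.10 to -0.30 and the Week 16 slope from -0.45 to -0.55, with linear steps between. The implied total SD at Week 16 for a slope of -0.50 is √(0.81 + 0.25 × 0.64) = 0.985, close to the planned 1.0. With baseline-by-visit the SE is 0.9 × 0.1980 = 0.1782.

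**Constant residual SD.** With equal or serial correlation the weights are symmetric over visits, so c is the midpoint of the Week 4 and Week 16 slopes.

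- Mildest case, -0.30 to -0.45: c = -0.375 and the gap is 0.075. SE ratio = √(1 + 0.075² × 0.64/0.81) = 1.002.
- Steepest case, -0.10 to -0.55: c = -0.325 and the gap is 0.225. SE ratio = √(1 + 0.225² × 0.64/0.81) = 1.020.

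**Growing residual SD, one case in full.** Take SDs of 0.6, 0.7, 0.8 and 0.9, serial correlation 0.7, and slopes of -0.15, -0.25, -0.35 and -0.45. The weights are 0.693, 0.077, 0.066 and 0.164. Then c = -(0.104 + 0.019 + 0.023 + 0.074) = -0.220 and the gap is 0.230. SE ratio = √(1 + 0.230² × 0.64/0.81) = 1.021, so the SE is 0.182 against 0.178. Of each 0.1-point imbalance, 0.023 stays.

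**Range.**

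| Residual SD over visits | SE at Week 16, one slope against baseline-by-visit | Left uncorrected per 0.1-point imbalance |
|---|---|---|
| Constant | about 0% to 2% larger | 0.01 to 0.02 |
| Growing (Week 4 SD 0.45 or 0.6) | about 1% to 11% larger | 0.01 to 0.05 |
| Any, equal slopes | no loss | 0 |

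The growing-SD row assumes moderate within-patient correlation. Very strong and equal correlation between visits would push its upper end higher.

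**Power.** At an 11% larger SE, 0.1782 × 1.11 = 0.198, and power at a difference of 1.0 is again 99.90%. Power would reach 99% only at SE = 1/(1.960 + 2.326) = 0.233, which is 31% above 0.1782.

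**Likely imbalance.** A simulation with 120 and 40 patients and baseline SD of about 0.67, taking Visit 2 HbA1c as equal to baseline, gave an imbalance SD of 0.07 points with stratification and 0.12 without. At 0.07, between 0.07 × 0.1 = 0.007 and 0.07 × 0.5 = 0.035 points would stay in the Week 16 difference.

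**The case against.** The strongest reply is that the documents supply none of the figures on which the size depends. Protocol 5.4 speaks of when the mean response is stable. It says nothing about baseline slopes or residual variance by visit. That stands, and the point must stay conditional.

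Several stronger readings are tempting and are not supported:

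- A reader might infer that Week 16 is in effect adjusted with the Week 4 slope. That needs both steepening slopes and residual variance that grows over visits. With constant variance the pooled slope lies midway.
- A reader might infer that most of any baseline imbalance is kept. In the constant-SD cases the share is 0.0075/0.045 = 17% to 0.0225/0.055 = 41%. Only the steep cases with growing SD keep most of it.
- A reader might infer bias. With complete data, randomization keeps the estimate unbiased on average, and the leftover is conditional on chance imbalance. Stratification on Visit 2 HbA1c limits that imbalance. Dropout that depends on baseline was not modelled in the figures above.
- A reader might infer that the MMRM and the ANCOVA will disagree because of the slope. The ANCOVA also carries the last observation forward, so they can differ for that reason alone, and no discrepancy was shown.

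**Conclusion.** The concern holds in conditional form. The primary model as written has one baseline slope, and the Week 16 contrast is adjusted with it. If slopes steepen over visits, the cost is some precision and some correction for imbalance, within the ranges tabulated above. Those ranges rest on assumed slopes, SDs and correlations and on complete data at Visits 4 to 7.

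This is a free improvement to the specification. It does not threaten the trial's conclusion: the leftover from a typical stratified imbalance is at most about 0.035 points against a planned difference of 1.0, and the stated power is untouched. The same argument could be made for fasting serum glucose and body weight, but it was not demonstrated for them.

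**What to change.** Add a baseline HbA1c-by-visit interaction to the primary MMRM in Protocol 10.3.3.1 and SAP 5.10.1.2, and align the model description in the Protocol synopsis. The per-protocol repeat of the model would then carry the term too.

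The cost is three parameters (four visit-specific slopes in place of one) with about 136 expected completers. No new data, visits or patients are needed. If the slopes turn out equal, the price in precision is negligible.

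Extending baseline-by-visit to the glucose and weight MMRMs in SAP 5.10.2 is optional. That section does not list visit or treatment-by-visit for those models, so its wording should be completed in any case.

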#### 5.10.1.3. Secondary Analysis Model

The secondary analysis for the primary endpoint will be an ANCOVA for HbA1c change from baseline to the Week 16 endpoint with treatment, and insulin regimen (basal insulin, premixed insulin, or basal/mealtime insulin) as fixed effects and baseline HbA1c as a covariate, with missing endpoints imputed with last observation carried forward (LOCF) using postbaseline data only. If there are no data after the date of randomization, the endpoint will be considered missing.

#### 5.10.2. Secondary Efficacy Analysis

Secondary efficacy measures that are continuous variables (changes from baseline) other than HbA1c will be analyzed using MMRM on the FAS. The MMRM model will include treatment, baseline HbA1c (<8.5%,  $\geq8.5\%$ ), and insulin regimen (basal insulin, premixed insulin, or basal/mealtime insulin) as fixed effects and a covariate of baseline value. Also, the ANCOVA models will include treatment, baseline HbA1c (<8.5%,  $\geq8.5\%$ ), and insulin regimen (basal insulin, premixed insulin, or basal/mealtime insulin) as fixed effects and a covariate of baseline value.

#### 5.10.2.1. Percentage of Patients Achieving HbA1c of <7.0% and ≤6.5%

Analysis of patients achieving HbA1c levels <7.0% or  $\le 6.5\%$  based on repeated measures logistic regression with generalized linear mixed model will be summarized by treatment group using FAS. The model will include independent variables of treatment, insulin regimen (basal insulin, premixed insulin, or basal/mealtime insulin), visit, and treatment-by-visit interaction as fixed effects, and baseline HbA1c as a covariate.

#### 5.10.2.2. Analysis of Fasting Serum Glucose (FSG)

Summary and analysis of FSG based on MMRM will be displayed by treatment group using FAS.

#### 5.10.2.3. Analysis of 7-point SMPG profile

The 7-point SMPG profiles before and 2 hours after breakfast, before and 2 hours after lunch, before and 2 hours after dinner, and bedtime will be obtained within 2 weeks prior to corresponding visit. In general, the mean of the two daily mean values will be used for reporting purpose. If the value from either day is missing, then the non-missing value will be used as the mean of the two daily mean values. Also, if both two daily mean values are missing then the mean of the two daily mean values will be missing. The daily mean is calculated as the mean of available values collected on a particular day.

The following variables for 7-point SMPG profile will be analyzed using ANCOVA model with missing endpoints imputed with LOCF:

- 1. Pre morning meal PG (mg/dL)
- 2. 2-hour postprandial measurement for morning meal PG (mg/dL)
- 3. Pre midday meal PG (mg/dL)
- 4. 2-hour postprandial measurement for midday meal PG (mg/dL)
- 5. Pre evening meal PG (mg/dL)
- 6. 2-hour postprandial measurement for evening meals PG (mg/dL)
- 7. Bedtime BG (mg/dL)
- 8. Morning meal 2-hr excursion (mg/dL)
- 9. Midday meal 2-hr excursion (mg/dL)
- 10. Evening meal 2-hr excursion (mg/dL)
- 11. Mean of all meals 2-hr excursion
- 12. Mean of all 7-point PG (mg/dL)
- 13. Mean of all pre-meals PG (mg/dL)
- 14. Mean of all postprandial meals PG (mg/dL)
- 15. Circadian variation in 7-point PG (mg/dL)

For before and 2 hours after meal, and bedtime PG (reports 1-7), the mean PG value at each visit is calculated as the average of 2 daily PG values. The change from baseline is calculated as the mean PG value at endpoint minus the mean PG value at the baseline.

For the morning, midday and evening meal 2-hr excursion (reports 8-10), the daily excursion for each meal is calculated as the postprandial meals PG minus the fasting plasma glucose (FPG). The mean glucose excursion for each meal at each visit is calculated as the average of 2 daily glucose excursions. The change from baseline is calculated as the mean excursion at endpoint minus the mean excursion at baseline.

For mean of all meals 2-hr excursion at each visit (report 11), the daily mean for all meals is calculated as the average of glucose excursion for morning, midday and evening meals on a particular day. The mean of all meals 2-hr excursion at each visit is calculated as the average of 2

daily means. The change from baseline is calculated as the mean of all meals 2-hr excursion at endpoint minus the mean of all meals 2-hr excursion at baseline.

For mean of all 7-point PG (report 12), the daily mean is calculated as the average of 7 PG values collected on a particular day. The mean of all 7-point PG at each visit is calculated as the average of 2 daily means. The change from baseline is calculated as the mean of all 7-point PG at endpoint minus the mean of all 7-point PG at baseline.

For mean of all pre-meals PG (report 13), the pre-meal daily mean is calculated as the average PG values collected for pre-morning, pre-midday and pre-evening meals on a particular day. The mean of all pre-meals PG at each visit is calculated as the average of 2 pre-meal daily means. The change from baseline is calculated as the mean of all pre-meals PG at endpoint minus the mean of all pre-meals PG at baseline.

For mean of all postprandial meals PG (report 14), the post-meal daily mean is calculated as the average of 2-hr postprandial meals PG values of morning, midday and evening meals on a particular day. The mean of all postprandial meals PG at each visit is calculated as the average of 2 post-meal daily means. The change from baseline is calculated as the mean of all postprandial meals PG at endpoint minus the mean of all postprandial meals PG at baseline.

For circadian variation in 7-point PG (report 15), the daily circadian variation is calculated as the difference between maximum and minimum (maximum - minimum) PG values collected on a particular day. The mean circadian variation at each visit is calculated as the average of 2 daily circadian variation. The change from baseline is calculated as the circadian variation at endpoint minus the circadian variation at baseline.

Fasting PG during follow-up period will be plotted by patient.

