**Study Schedule, Protocol H9X-JE-GBGF**

- f For each parameter, 3 measurements will be taken 30 seconds apart using the same arm. An appropriately sized cuff (cuff bladder encircling at least 80% of the arm) should be used to ensure the accuracy of blood pressure (BP) measurements. The arm used for the BP measurement should be supported at heart level.
- g A single 12-lead ECG will be performed locally and recorded, after the patient has been lying supine for 5 minutes. If the subject has a single 12-lead ECG record which was performed within 3 months prior to Visit 1, the data can be used as a baseline measurement.
- h Serum pregnancy test to be performed by the central lab at Visits 1 and 3 for women of childbearing potential only. Subsequent pregnancy tests can be performed as required at local laboratories. A local (urine) pregnancy test may additionally be performed at the investigator's discretion during the study.
- i Fasting laboratory samples must be obtained after a fast of 8 hours or more without eating, drinking (except for water), or performing any significant physical activity.
- j Patients are required to measure their fasting (pre-breakfast) plasma glucose (FPG) concentration at least once every 2 to 3 days at approximately the same time of day after Visit 3. By the investigator's decision, the frequency of measurement of FPG could be increased.
- k 7-point SMPG profiles (blood glucose measurements before breakfast, lunch, dinner, and bedtime and 2 hours after breakfast, lunch, and dinner) should be performed on 2 days within the 2 weeks prior to Visit 3 (Week 0), Visit 7 (Week 16), and ET visit (only when the patient discontinued before Week 16).

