**Table GBGF.4.1. Objectives and Endpoints**

Objectives	Endpoints

Primary To show superiority of the addition of once-weekly dulaglutide 0.75 mg compared to the addition of once-weekly placebo to insulin treatment with or without 1 or 2 OADs, on change from baseline in HbA1c after 16 weeks of treatment in Japanese patients with T2D.
	
 
• The change in HbA1c from baseline to 16 weeks
 

Secondary For efficacy, to compare dulaglutide 0.75 mg to placebo at 16 weeks.
 
For safety, to compare dulaglutide 0.75 mg to placebo for 16 weeks.
 
To describe long-term efficacy of dulaglutide 0.75 mg in combination with insulin therapy up to 52 weeks.
 
To describe long-term safety of dulaglutide 0.75 mg in combination with insulin therapy up to 56 weeks (to include the follow-up period).
	
 
• Percentage of patients achieving HbA1c target values of <7.0% or ≤6.5% at 16 weeks
 
• The change in FSG (central laboratory) from baseline to 16 weeks
 
• The change in PG from 7-point SMPG profiles from baseline to 16 weeks
 
• The change in body weight from baseline to 16 weeks
 
• The change in insulin dose from baseline to 16 weeks
 
• TEAEs
 
• Incidence and rate of hypoglycemic episodes
 
• Adjudicated cardiovascular and pancreatic AEs
 
• Thyroid neoplasm AEs
 
• Allergic/hypersensitivity AEs
 
• Laboratory parameters of hematological safety and biochemical abnormalities
 
• Efficacy parameters described above
 
• Safety parameters described above
 

Exploratory Exploratory objectives are to assess the health outcomes variables at 16 and 52 weeks.
	
 
• Diabetes Treatment Satisfaction Questionnaire status (DTSQs)
 
• Diabetes Therapy Related Quality of Life (DTR-QOL)
 
• Device Questionnaire
 
• Dietary Evaluation
 

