#### 9.1.2. Secondary Efficacy Assessments

The following secondary efficacy measures will be evaluated at 16 and 52 weeks:

- Change from baseline in HbA1c (52 weeks)
- Percentage of patients achieving HbA1c targets of  $<7.0\%$  or  $\leq 6.5\%$ , as measured at the central laboratory
- Changes from baseline in FSG measured at the central laboratory
- Changes from baseline in PG from 7-point SMPG profiles
- Changes from baseline in body weight
- Changes from baseline in insulin dose

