- The Device Questionnaire is a self-administered questionnaire to assess the usability and preference of Ateos (the name of device for Trulicity in Japan) compared to the insulin device the patient has been using so far. The questionnaire consists of 2 sections. In the first section, patients will respond to 12 items about usability and preference using a 5-point scale (from “Strongly Agree” to “Agree” in insulin device, both devices are the same, and from “Strongly Agree” to “Agree” in Ateos). In the second section, patients are asked whether each procedure to prepare and inject was cumbersome or not for Ateos (3 procedures) and insulin device (6 items). The patients’ response is chosen from rarely, sometimes, or always cumbersome in each procedure. This questionnaire was developed by the study team based on the previous research (Bailey et al. 2011; Oyer et al. 2011).
- The Dietary Evaluation will explore the relationship between meal preference and efficacy of dulaglutide in Japanese patients with T2D. Patients are required to complete a meal record (picture and record sheet) on 2 days during the 2-week period immediately before: Visit 3 (Week 0), Visit 7 (Week 16), or Visit 12 (Week 52). The timing of the meal record should be on the same date as 7-point SMPG measurements (except for 52 weeks). The Lilly designated vendor will calculate the total fats, total carbohydrates, total protein, and caloric intake amount based on the meal record.

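### SAP 5.10.2.3 subtracts pre-breakfast glucose for every meal, so the midday and evening 2-hour excursions, and the all-meals mean, do not measure the meal excursion alone

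*SAP*

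**What the plan says.** For reports 8 to 10, SAP 5.10.2.3 states that "the daily excursion for each meal is calculated as the postprandial meals PG minus the fasting plasma glucose (FPG", closing the parenthesis after the abbreviation. The sentence covers all three meals. Report 11 is then built from these three results: "the daily mean for all meals is calculated as the average of glucose excursion for morning, midday and evening meals on a particular day".

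FPG is not defined in the SAP. The protocol does define it, in footnote j of the Schedule of Activities: "Patients are required to measure their fasting (pre-breakfast) plasma glucose (FPG) concentration".

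The values before lunch and dinner are collected (footnote k) and are variables in their own right in the same SAP section. Report 3 is listed as "Pre midday meal PG (mg/dL", with its unit in parentheses; report 5 is the evening counterpart. Report 13 combines them with the morning value: "the pre-meal daily mean is calculated as the average PG values collected for pre-morning, pre-midday and pre-evening meals on a particular day". Neither document gives another formula for the midday or evening excursion.

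A side point concerns timing. Protocol 9.1.2 introduces a list that includes the 7-point profile with "The following secondary efficacy measures will be evaluated at 16 and 52 weeks". Table GBGF.4.1 words the endpoint as "The change in PG from 7-point SMPG profiles from baseline to 16 weeks". The Schedule of Activities and footnote k have no Week 52 profile, and the dietary paragraph of Protocol 9.1.3 says "The timing of the meal record should be on the same date as 7-point SMPG measurements (except for 52 weeks".

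**The concern.** A variable labelled as a meal's 2-hour excursion should measure the rise from just before that meal to two hours after it. With pre-breakfast glucose as the reference for lunch and dinner, it also picks up whatever glucose did between the pre-breakfast reading and the reading before that meal.

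FPG is unlikely to be shorthand for a pre-meal value, because the section names the pre-midday, pre-evening and pre-meal values explicitly when it means them. If shorthand was intended, a programmer following the sentence would still subtract the wrong number.

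Reports 9 to 11 are compared between arms by ANCOVA, at a two-sided 0.05 level without multiplicity adjustment (SAP 5.2). A treatment effect on fasting glucose could therefore appear, with a p-value, as an effect on lunch and dinner excursions. The protocol's background section lists delayed gastric emptying and glucose-dependent insulin secretion among the drug's effects, so meal excursions are likely to be read with interest.

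**Working it through.** **Inputs.** The rule for reports 8 to 10, the construction of report 11, and reports 1, 3, 5, 13 and 14 come from SAP 5.10.2.3. The meaning of FPG comes from protocol footnote j. FPG is taken to be the pre-breakfast reading of the same profile day (report 1). The plan states no figure to reproduce, and the documents contain no SMPG data, so every mg/dL value below is an assumption.

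**Step 1: one meal.**

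post − FPG = (post − own pre-meal) + (own pre-meal − FPG)

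The last term is zero for breakfast. For lunch it is report 3 minus report 1, and for dinner report 5 minus report 1.

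**Step 2: mean over three meals, complete data.**

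- As written: mean(post) − FPG = report 14 − report 1.
- With each meal's own pre-meal value: mean(post) − mean(pre) = report 14 − report 13.
- Difference: report 13 − report 1.

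**Step 3: an assumed profile (mg/dL).** Pre/post values are 160/230 at breakfast, 180/240 at lunch and 190/250 at dinner.

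| | Morning | Midday | Evening | Mean |
|---|---|---|---|---|
| SAP rule | 230 − 160 = 70 | 240 − 160 = 80 | 250 − 160 = 90 | 80.0 |
| Own pre-meal | 230 − 160 = 70 | 240 − 180 = 60 | 250 − 190 = 60 | 63.3 |

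Check: report 14 = (230 + 240 + 250)/3 = 240 and report 13 = (160 + 180 + 190)/3 = 176.7. Then 240 − 160 = 80.0 and 240 − 176.7 = 63.3, as in the table.

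**Step 4: change from baseline.** Let both breakfast readings fall by 30, to 130/200, with lunch and dinner unchanged.

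- SAP rule: 70, 110, 120, mean 100. The changes are 0, +30, +30 and +20.
- Own pre-meal: 70, 60, 60, mean 63.3. Nothing changes.

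A better fasting value is thus recorded as worse lunch and dinner excursions. If all readings fall by 30, neither version changes. The extra term cancels only when fasting and later pre-meal values move together.

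**Step 5: treatment effect.** Let d1, d3 and d5 be the treatment effects on pre-morning, pre-midday and pre-evening glucose. The expected distortion is:

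- report 8: 0
- report 9: d3 − d1
- report 10: d5 − d1
- report 11: (d3 + d5 − 2·d1)/3, the report 13 effect minus the report 1 effect

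With the same gap g = d3 − d1 = d5 − d1 at both meals, report 11 shifts by 2g/3:

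| Assumed g (mg/dL) | −20 | −10 | 0 | +10 | +20 |
|---|---|---|---|---|---|
| Reports 9 and 10 | −20 | −10 | 0 | +10 | +20 |
| Report 11 | −13.3 | −6.7 | 0 | +6.7 | +13.3 |

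If the gap exists at one meal only, report 11 shifts by g/3 (3.3 for g = 10, 6.7 for g = 20).

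**The case against.** The strongest reply is that the SAP gives an explicit, reproducible rule and that neither document defines an excursion as relative to the meal's own starting value. On that view reports 9 to 11 are valid measures of rise above fasting under a loose label. A deliberate choice is possible, but the SAP gives no reason for it and the labels say otherwise. The text would still need to change, by naming the FPG reference and renaming the variables.

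The second reply is that little is at stake. The protocol endpoint is the change in glucose from the profiles and does not name excursions. The pre-meal and post-meal values are reported separately (reports 1 to 6, 13 and 14), and the distortion is zero if treatment moves all pre-meal values equally. This stands as a limit on severity. A reader could approximate the own-meal point estimate by subtraction, but not its confidence interval or p-value, which need the within-patient covariance.

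Two technical caveats also stand. Footnote j belongs to the daily fasting measurement, so equating FPG with report 1 of the profile is an inference, though the natural one. And the report 14 minus report 1 identity holds on complete data. With missing readings, and with each variable adjusted for its own baseline, the analysed estimates need not satisfy it exactly.

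Finally, the SAP's revision history says Version 3 added post hoc analyses. If results were already known, redefining a tested variable calls for open disclosure. That affects how the repair is made, not whether it is needed.

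**Conclusion.** The concern holds. As written, reports 9 and 10 and two of the three components of report 11 include the difference between that meal's pre-meal glucose and pre-breakfast glucose, and change from baseline does not remove it. The distortion is 1 mg/dL in report 9 or 10 for each 1 mg/dL by which the treatment effect on that meal's pre-meal glucose differs from the effect on fasting glucose. In report 11 it is 0.33 if one meal is affected and 0.67 if both are. Actual size and direction cannot be determined from the documents.

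The scope is 3 of 15 derived variables under one secondary endpoint. Report 8, the component glucose values and the primary HbA1c analysis are unaffected. This should be corrected, but it does not threaten the trial's main conclusion. The conclusion rests on reading FPG as the protocol defines it.

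The Week 52 mismatch in Protocol 9.1.2 is a minor wording conflict, not a lost endpoint.

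**What to change.** In SAP 5.10.2.3, define each daily excursion as the 2-hour value minus the pre-meal value of the same meal on the same day: report 2 minus 1, report 4 minus 3, and report 6 minus 5. Keep report 11 as the daily mean of the three. This changes one sentence; all inputs are already collected, so no data or visits are added. If results have already been seen, describe and justify the change in the clinical study report. If the fasting reference was intended, state that and rename reports 9 to 11.

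Separately, limit the 7-point profile in Protocol 9.1.2 to Week 16. Do the same under the long-term efficacy objective, whose endpoint refers back to the full list of efficacy parameters. This is a wording correction to match the schedule.
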